## 6.1 Screening Assessment

Before initiating any screening activities, the scope of the study will be explained to each patient during informed consent. Patients should be advised of any known risks inherent in the planned procedures, any alternative treatment options, their right to withdraw from the study at any time for any reason, and their right to privacy. After this explanation, patients should be asked to sign and date a Notice of Privacy Practice research authorization/HIPAA form and an IRB-approved statement of informed consent that meets the requirements of the Code of Federal Regulations (Federal Register Vol. 46, No. 17, January 27, 1981, part 50). During the screening period, subject eligibility will be determined according to the inclusion and exclusion criteria (Section 4.1,4.2). The following assessments will be performed during this time:

- Obtain informed consent and research authorization
- Inclusion/Exclusion Criteria
- Record demographics (including age) and medical history
  
- Physical exam
- Urine or Blood Pregnancy test (within 14 days for women of child bearing potential)
- Discuss and record concomitant medications
- ECOG performance status, vital signs [body temperature, blood pressure, pulse, respiratory rate, weight, height]
- Obtain histologic or (if appropriate) radiologic confirmation of disease
- Confirm eligibility according to the inclusion/exclusion criteria
- Laboratory tests (within 28 days of enrollment):
  - Hematology (CBC with diff)
  - Blood Chemistry
    - Creatinine, AST, AT, ALK Phos T Bili > 2.5 x ULN (all are SOC)
- If possible, baseline caloric intake assessment using a dietary log mediated by a nutritionist. This will take place at the patient's baseline assessment if possible and may be done via a phone interview.
  - If caloric intake is completed, a calculation of the patient's estimated caloric needs via the Harris-Benedict Equation will be performed.

## 6.2 Treatment Period (Week 1 Day 1 – day prior to Surgical Resection)

After screening is completed and eligibility is confirmed, Metformin and Doxycycline will be ordered by a study investigator and the medication will be dispensed by the Investigation Drug Service pharmacy. The date subjects begin taking metformin and doxycycline will be considered Week 1 Day 1, and a return to clinic is not necessary. Surgical resection will be scheduled a minimum of 7 days after the start of metformin and doxycycline and maximum of 5 weeks. The participant will receive a Patient Medication Diary to record the time (AM and PM) and number of pills to take for both Metformin and Doxycycline.

See Study Calendar (Section 6 above) for when the following assessments will be performed during the treatment period:

- Study Treatment:
  - Metformin
  - Doxycycline
- Study treatment follow-up phone calls (Day 3  $\pm$ 2 days and Day 5  $\pm$ 2 days from start of medication, and weekly thereafter until surgical resection)
- Concomitant medications

- Adverse event assessment

### 6.3 Surgical Resection

The following study activities will occur on the day of surgical resection:

- Two SST red-top tubes of blood for correlative studies: oncomiR miR-21, serum triglycerides, IGF-1, IGF-BP3, ESR, adiponectin, leptin, IGF-1R, exosome evaluation, metabolomics profile, and microRNA expression profile.
- Definitive cancer surgery
  - Pathology report needed
  - Tumor tissue
    - Exosome evaluation, metabolomics profile, and microRNA expression profile.
- Return all Metformin and Doxycycline medication bottles (including any unused tablets/pills)
- Collection of pill diaries

### 6.4 End of Treatment Study Visit (Within 21 Days $\pm 7$ of stopping protocol study medications)

The following study activities will occur at End of Treatment Visit after patients have completed treatment with metformin and doxycycline:

- Physical exam
- Vital signs
- ECOG performance status
- Concomitant medications
- Adverse event assessment

### 6.5 Long term Follow-up

A follow up phone call will be performed 30 days ( $\pm 5$  days) after the last dose of metformin and doxycycline for any other side effects or adverse events. This is allowed to coincide with the End of Treatment study visit if it occurs during timing overlap. Subjects will be followed for 12 months following the End of Treatment visit or until death. Subjects withdrawn from the study because of AEs will be followed until the adverse event has either resolved or stabilized. Reasons for premature withdrawal should be determined and noted.

The participant's medical records will be reviewed every 3 months ( $\pm 1$  month) for 12 months to assess overall survival and final pathologic staging.

## 7 Study Procedures and Evaluations

The Trial Flow Chart- Section 6 summarizes the trial procedures to be performed at each visit. Individual trial procedures are described in detail below. It may be necessary to perform these procedures at unscheduled time points if deemed clinically necessary by the investigator. Tumor biopsies will be formalin fixed and paraffin embedded. If a confirmatory diagnostic core biopsy is required and there is excess tissue available not needed in the course of clinical care, this tissue will be flash frozen in liquid nitrogen. When a pre-treatment sample has been acquired in this manner, and if there is excess tissue is available at the time of resection, these tissue samples will also be frozen in liquid nitrogen as well.

When possible, a registered dietician will meet with the patients within the first seven days of enrollment and through an interview record their last 3 days of caloric intake per their recollection and record this on a specific case report form. The dietician will also then use their height, weight, age, gender, and self-reported activity level per the Harris Benedict Equation to estimate their caloric intake versus their caloric needs.

Serologic Analysis of the metabolic profile of the patients will be performed at the time of enrollment and the time of resection. Two serum separator tubes of blood will be collected and transported at room temperature before being stored at -4 degrees C in a locked refrigerator.

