**\* If surgery is scheduled past Day 8, patients will stay on metformin and doxycycline until the day prior to surgery.**

- a. Metformin will be given initially with a starting dose of 500mg once a day for Days 1-3.
- b. Metformin will be increased to 500 mg orally twice a day for Days 4-6
- c. If tolerated, beginning Day 7 metformin will be increased to 1000 mg twice a day. Subjects will maintain the maximum tolerated dose (up to 1000 mg twice daily) until the day prior to their scheduled definitive surgery.
- d. When possible, baseline biopsy tissue is to be obtained prior to starting study medications. Two serum separator tubes of serum will be taken at the same time as the biopsy specimen (if possible), otherwise done at time of consent. If a pre-treatment sample has already been acquired and flash froze and if there is excess tissue available at resection, the second specimen will also have a piece flash frozen for metabolomic testing.
- e. Doxycycline will be taken once every 12 hours, with the last dose being taken at least 12 hours prior to scheduled time of definitive surgery.

Metformin and doxycycline are the therapeutic agents. For metformin, the initial starting dose will be 500 mg orally daily for 3 days which will then be increased to 500 mg orally twice daily, and if tolerated, further increased to 1000 mg twice daily after day 6. Subjects will maintain the maximum tolerated dose (up to 1000 mg twice daily) until the day prior to their scheduled definitive surgery.

For doxycycline the patients will take 100 mg by mouth every twelve hours until the day prior to their surgery.

**Criteria for  
Evaluation:**

Primary:

- Assess the impact of metformin and doxycycline on the percentage of cancer associated fibroblasts that stain with 1+ intensity or greater for CAV1 by immunohistochemistry (IHC) pre and post metformin and doxycycline exposure as determined by two blinded pathologists. All patients from whom samples are obtained both pre- and post-treatment will be included in the primary analyses.

Secondary:

- Assess the impact of metformin and doxycycline on the percentage of cancer-associated fibroblasts that express MCT4 and the percentage of cancer cells that express MCT1 and TOMM20. All patients from whom samples are obtained both pre- and post-treatment will be included in the secondary analyses.

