- Assess safety and tolerability of metformin and doxycycline treatment in subjects with cancer. Toxicity will be evaluated using the most recent version (version 4) of the NCI toxicity criteria, i.e. the NCI Common Terminology Criteria for Adverse Events (CTCAE) version 4.03.
- The staining patterns of CAV1, MCT4, MCT1, and TOMM20 will be compared to the ER, PR, and Her2 expression levels whenever these markers have been performed in the course of clinical care. All patients from whom samples are obtained both pre- and post-treatment will be included in the secondary analyses

Correlative:

- Mass spectroscopy imaging (MSI) will be performed on paired samples, comparing metabolite profiles in the pre-treatment and post-treatment tumor sample. MSI allows assessment of metabolite levels in spatially defined tumor regions and hence will allow the evaluation of metabolite levels in carcinoma and stromal cell compartments. Only patients for whom flash frozen samples can be

obtained both prior to initiation of treatment and in the OR at the time of resection will be considered for this analysis.

- Patients who are able to complete, when possible, a 3 day recall dietary diary with the aid of a nutritionist will also have their caloric needs estimated with a Harris-Benedict Equation.
- Patients from whom serum samples are available will be assessed for oncomiR-21, IGF1, IGF-BP3, ESR, adiponectin, leptin, IGF-1R, and exosome and metabolomics profiles in exploratory analyses.

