### 2.1.3 Correlative

- To assess the effect of combined metformin and doxycycline therapy on the metabolic profile of cancer cells and stroma using mass spectroscopy imaging (MSI) on paired samples, comparing metabolite profiles in the pre-metformin and post-metformin tumor sample.
- To assess, when possible, the impact of a patient's nutritional status, estimated using 3-day dietary recall versus caloric needs as calculated by the Harris-Benedict equation on the baseline and net change in CAV1.
- To assess the effect of combined metformin and doxycycline therapy on oncomiR miR-21 after intervention.
- To assess the effect of combined metformin and doxycycline therapy on adipokines and the IGF-1/insulin signaling pathways through assessment of serum triglycerides, IGF-1, IGF-BP3, erythrocyte sedimentation rate (ESR), adiponectin, leptin, IGF-1R, exosome evaluation, metabolomics profile, and microRNA expression profile.

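### ESR is assigned to serum separator tubes that cannot yield it, and the storage line for the correlative blood contradicts itself; only exploratory correlatives are affected

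*Combined protocol and SAP*

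**What the plan says.** ESR is a listed analyte of the correlative objective. Section 2.1.3 and the Study Summary objectives include it in the panel "serum triglycerides, IGF-1, IGF-BP3, erythrocyte sedimentation rate (ESR), adiponectin, leptin, IGF-1R, exosome evaluation, metabolomics profile", and Table 3 lists it under Correlatives.

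The blood for this panel is specified as follows.

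- Baseline (Study Summary, study design note d, repeated under Table 1): "Two serum separator tubes of serum will be taken at the same time as the biopsy specimen (if possible), otherwise done at time of consent".
- Day of surgery (Section 6.3): "Two SST red-top tubes of blood for correlative studies: oncomiR miR-21, serum triglycerides, IGF-1, IGF-BP3, ESR", followed by the rest of the panel, including exosomes, metabolomics and microRNA.
- Handling at both time points (Section 7): two serum separator tubes, which are "transported at room temperature before being stored at -4 degrees C in a locked refrigerator".
- Analysis set (Study Summary, Criteria for Evaluation, which labels this work exploratory): "Patients from whom serum samples are available will be assessed for oncomiR-21, IGF1, IGF-BP3, ESR, adiponectin, leptin, IGF-1R, and exosome and metabolomics profiles in exploratory".

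The Section 6 calendar marks hematology and chemistry at screening only. The visit descriptions in Section 3 give the number and volume of blood vials but no tube type.

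**The concern.** Two written instructions fail when followed exactly.

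The first concerns ESR. A serum separator tube lets the blood clot and then separates the serum from the cells. ESR needs red cells suspended in unclotted blood, so the named tube cannot supply the named test.

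The second is the storage line. A refrigerator holds samples above freezing, and -4 °C is below it. Staff cannot tell whether to chill or freeze the tubes. Section 7 sets no limit on time at room temperature and describes no spin or aliquot step, although the samples are meant for metabolomics, exosomes and microRNA. The same section sends tissue to liquid nitrogen.

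At stake is a correlative objective that rests on within-patient change from baseline to surgery. A pre-treatment draw cannot be repeated once dosing has begun, so a handling error at baseline loses that patient's pair.

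**Working it through.** The plan states no figure on this point, so the check is mainly a comparison of sections.

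**1. Can ESR be obtained as a pair?**

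- Baseline: two serum separator tubes (design note d; Section 7). No other correlative tube is named.
- Surgery: two serum separator tubes, with ESR assigned to them by name (Section 6.3).
- Criteria for Evaluation ties ESR to patients with serum available.
- Other blood: the CBC would normally use an anticoagulated tube, but the calendar places it at screening only. It could serve baseline at most, and the plan does not link it to ESR.

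Planned enrollment is 2 × 23 = 46. No suitable tube is planned at surgery, so the number of ESR pairs is 0 of up to 46. This step uses one fact from general laboratory knowledge, not from the documents: ESR requires unclotted whole blood. That is what the test measures and does not depend on stability data.

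**2. Is the storage line workable?**

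The temperature and the equipment disagree. If the minus sign is a slip, the tubes are chilled; if the equipment word is the slip, they are frozen. Nothing else in the documents decides between the two. Time to storage, separation, aliquoting and storage duration are not given.

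**3. Could storage differ between the two samples of a pair?**

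Inputs:

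- e, planned exposure: 7 to 35 days (Section 1.2, dosage rationale; Section 6 note D gives 7 days to 5 weeks, and 5 × 7 = 35).
- s, time from baseline draw to Day 1: zero or more, since Section 7.3.1 allows the draw at any time in screening up to Week 1 Day 1.

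If both samples are assayed on the same date (an assumption), the baseline sample has been stored longer by s + e. With s = 0 this is 7 days at the shortest exposure and 35 days at the longest; any screening interval adds to it. If each sample is assayed after the same delay from its own draw, the difference is 0.

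The documents do not say which applies. Under the first, any drift would run in the same direction as the pre/post contrast in every patient. No untreated serum comparator is planned (the controls in the endpoint rationale of Section 1.2 are tumor-bank samples), so drift could not be separated from treatment.

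**4. Does this touch the main analysis?**

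No. Section 10.4 bases the sample size on a 20% increase in CAV1 staining with a standard deviation of 32%. A one-sided paired t-test needs 18; dividing by the Wilcoxon efficiency 3/π gives 18.85, so 19; and 19/0.85 = 22.4, so 23. Both stated figures reproduce, and neither uses serum data.

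**The case against.** The strongest reply is that these are slips in the description of exploratory work and that laboratory detail belongs elsewhere. Section 7.3 refers to a Procedures Manual that was not available for this review. It is cited for blood amounts by visit and sample type, but spin times and aliquoting are ordinary manual content, so their absence here does not show that the study lacks them. This stands for the processing detail. It does not rescue the explicit text: a manual that named another tube or temperature would conflict with Sections 6.3 and 7, which would still need correction.

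A reader might go further and infer that the serum panel as a whole cannot be delivered. The documents do not support that. Only ESR is ruled out by the tube itself. Whether triglycerides, the IGF markers, adipokines, microRNA, exosomes or metabolites survive this storage depends on stability data that the documents do not contain.

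A reader might also infer that the paired serum changes are confounded by storage. That is not established either. It needs unequal storage times, for example through batching, and batching is never stated. Section 7 places the serologic analysis at enrollment and at resection, which can be read as an assay close to each draw. Both draws otherwise share the same handling text.

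**Conclusion.** The point holds in limited form. As written, ESR cannot be obtained as a pre/post pair: 0 of up to 46. The storage instruction contradicts itself and has to be corrected before it can be followed. Both are stated rules that fail, not merely missing detail. The ESR conclusion assumes only that the tubes named are the tubes drawn and that ESR requires unclotted blood.

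Unequal storage is a possible risk, conditional on pairs being assayed together; the gap would then be at least 7 to 35 days. The size and direction of any resulting shift are unknown, and no bias is claimed.

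The consequence is confined to exploratory correlatives. The CAV1 primary endpoint, the MCT4, MCT1 and TOMM20 secondary endpoints, safety and the sample size do not depend on these tubes. The correction is still worthwhile because it is cheap and the baseline samples cannot be replaced.

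**What to change.** 1. Decide on ESR. Either delete it from the Study Summary (objectives and Criteria for Evaluation), the endpoint rationale in Section 1.2, Sections 1.3, 2.1.3 and 6.3, and Table 3; or add one anticoagulated tube at both existing correlative draws, read ESR fresh, and stop describing it as a serum assay. If it is kept, design note d and Sections 3, 6.3, 7 and 7.3.1 should name the tube.
2. In Section 7, replace the -4 °C refrigerator line with separation within a stated time, aliquoting, and a defined freezer temperature suited to the assays (for example -80 °C, to be confirmed by the assay laboratories).
3. State that each patient's pre- and post-treatment aliquots are assayed in the same run, and record collection and freeze times so that storage time can be examined. Same-run assay removes run-to-run differences within a pair but makes storage times unequal by the interval between draws, so it should go together with item 2.

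Cost: protocol and laboratory-manual wording, aliquoting and freezer space, plus one small tube per draw if ESR is kept. No visit is added.

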## **7.1 Administrative Procedures**

### **7.1.1 Informed Consent**

The Investigator must obtain documented consent from each potential subject prior to participating in a clinical trial. Consent must be documented by the subject's dated signature on a consent form along with the dated signature of the person conducting the consent discussion. A copy of the signed and dated consent form should be given to the subject before participation in the trial. The initial informed consent form, any subsequent revised written informed consent form and any written information provided to the subject must receive the IRB/ERC's approval/favorable opinion in advance of use. The subject should be informed in a timely manner if new information becomes available that may be relevant to the subject's willingness to continue participation in the trial. The communication of this information will be provided and documented via a revised consent form or addendum to the original consent form that captures the subject's dated signature.

### **7.1.2 Inclusion/Exclusion Criteria**

All inclusion and exclusion criteria will be reviewed by the investigator or qualified designee to ensure that the subject qualifies for the trial. Eligibility will be confirmed prior to the patient starting study medication.

### **7.1.3 Medical History**

A medical history will be obtained by the investigator or qualified designee. Medical history will include all active conditions, and any condition diagnosed within the prior 10 years that are considered to be clinically significant by the Investigator. Details regarding the disease for which the subject has enrolled in this study will be recorded separately and not listed as medical history.

### **7.1.4 Prior and Concomitant Review**

#### **Prior Medication**

The investigator or qualified designee will review prior medication use, including any protocol-specified washout requirement, and record prior medication taken by the subject within 28 days before starting the trial. Treatment for the disease for which the subject has enrolled in this study will be recorded separately and not listed as a prior medication.

#### **Concomitant Medications/Therapies**

The investigator or qualified designee will record medication, if any, taken by the subject during the trial. All medications related to reportable SAEs and ECIs should be recorded as defined in Section 7.2.

### **7.1.5 Disease Details and Treatments**

#### **Prior Cancer History**

The investigator or qualified designee will obtain prior and current details regarding disease status.

### **Prior Cancer Treatment**

The investigator or qualified designee will review all prior cancer treatments including systemic treatments, radiation and surgeries.

### **Subsequent Anti-Cancer Therapy Status**

The investigator or qualified designee will review all new anti-neoplastic therapy initiated after the last dose of trial treatment. If a subject initiates a new anti-cancer therapy within 30 days after the last dose of trial treatment, the 30 day Safety Follow-up visit must occur before the first dose of the new therapy. Once new anti-cancer therapy has been initiated the subject will move into follow-up.

## **7.2 Clinical Assessment**

### **7.2.1 Adverse Event (AE) Monitoring**

The investigator or qualified designee will assess each subject to evaluate for potential new or worsening AEs as specified in the Trial Flow Chart (Section 6) and more frequently if clinically indicated. Adverse experiences will be graded and recorded throughout the study and during the follow-up period according to NCI CTCAE Version 4.03 (see Section 8.3). Toxicities will be characterized in terms of seriousness, causality, toxicity grading, and action taken with regard to trial treatment. Please refer to Section 8.2 for detailed information regarding the assessment and recording of AEs.

### **7.2.2 Physical Examination**

The investigator or qualified designee will perform a physical examination during the screening period. Clinically significant abnormal findings should be recorded as medical history. A physical examination will be performed at the end of therapy study visit as specified in the Trial Flow Chart (Section 6.0).

### **7.2.3 Vital Signs**

The investigator or qualified designee will take vital signs at screening, and at the end of therapy study visit as specified in the Trial Flow Chart (Section 6.0). Vital signs should include temperature, pulse, respiratory rate, weight and blood pressure. Height will be measured at screening only.

